### 3.5.2.2. Systemic Events Endpoints

Subjects will be asked to assess severity of each systemic event according to Table 12 below.

**Table 12. Grading of Systemic Events**

	Grade 1 (Mild)	Grade 2 (Moderate)	Grade 3 (Severe)
Vomiting	1 to 2 times in 24 hours	>2 times in 24 hours	Requires IV hydration
Diarrhea	2 to 3 loose stools in 24 hours	4 to 5 loose stools in 24 hours	6 or more loose stools in 24 hours
Headache	Does not interfere with activity	Some interference with activity	Prevents daily routine activity
Fatigue	Does not interfere with activity	Some interference with activity	Prevents daily routine activity
Chills	Does not interfere with activity	Some interference with activity	Prevents daily routine activity
Muscle pain (other than muscle pain at the injection site)	Does not interfere with activity	Some interference with activity	Prevents daily routine activity
Joint pain	Does not interfere with activity	Some interference with activity	Prevents daily routine activity

Abbreviation: IV = intravenous.

Severe vomiting will be queried and if confirmed as an error will be excluded from the analysis.

Oral temperature will be recorded in the e-diary, in the evening, daily for 7 days after each vaccination and at any time during the 7 days when fever is suspected. The highest temperature for each day will be recorded as well. The protocol defines fever as an oral temperature  $\geq 38.0^{\circ}\text{C}$  ( $\geq 100.4^{\circ}\text{F}$ ), with severity scales shown in Table 13 and Table 14.

**Table 13. Severity Scale for Fever for Stage 1**

38.0-38.4°C
38.5-38.9°C
39.0-40.0°C
>40.0°C

**Table 14. Severity Scale for Fever for Stage 2**

38.0-38.4°C
>38.4-38.9°C
>38.9-40.0°C
>40.0°C

Temperatures <35.0°C and >42.0°C will be excluded from the analysis.

The original temperature scale (Table 13) was used in Stage 1 reporting and the updated temperature scale (Table 14) will be used in Stage 2 analyses.

For each systemic event, the following variables will be available similar to local reactions:

1. Each systemic event on each day (Days 1 to 7) after each vaccination.
2. Each systemic event on any day (Days 1 to 7) after each vaccination and any vaccination.
3. Any systemic event on any day (Days 1 to 7) after each vaccination and after any vaccination.
4. Maximum severity of each systemic event on any day (Days 1 to 7) after each vaccination and any vaccination.
5. Maximum duration of each systemic event after each vaccination.

The derivation of these variables is similar to the derivation of the variables for local reactions (Section 3.5.2.1).

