7.4.2. Systemic Events

7.4.2.1. Temperature

A digital thermometer will be given to the parent(s)/legal guardian or the subject with instructions on how to measure the subject's oral temperature at home. Oral temperature will be collected at in the evening daily for 7 days (Day 1 to Day 7) after each vaccination, and at any time during the 7 days when fever is suspected. The highest temperature for each day will be recorded in the e-diary. Fever is defined as temperature of $\geq 38.0^{\circ}\text{C}$ (100.4°F).

Temperature will be measured and recorded to 1 decimal place and then categorized according to the severity scale in Table 9:

Table 9. Severity Scale for Fever

Temperature 38.0°C to 38.4°C (100.4°F to 101.1°F)
Temperature 38.5°C to 38.9°C (101.2°F to 102.0°F)
Temperature 39.0°C to 40.0°C (102.1°F to 104.0°F)
Temperature $>40.0^{\circ}\text{C}$ ($>104.0^{\circ}\text{F}$)

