**Table 1. Summary of Major Changes in SAP Amendments**

Version / Date	Associated Protocol Amendment	Rationale	Specific Changes
4 17MAY2021	Amendment 2, 09JUL2019	Protocol Amendment	
 
• Moved the booster dose safety endpoints from secondary to primary safety endpoints.
 
• Moved some immunogenicity endpoints (related to persistence evaluation) from secondary to exploratory endpoints.
 
• Removed the 1:4 endpoint for ACWY strains for the persistence and booster endpoints.
 
• Updated the Stage 2 enrollment, for ACWY-experienced subjects in addition to ACWY-naïve subjects to obtain data on the persistence of the immune response after 2 doses of Neisseria meningitidis group A, B, C, W, and Y vaccine (MenABCWY) as well as on the safety and immunogenicity of the booster response in individuals who had previously received an ACWY-containing vaccine.
 
• Removed the persistence and booster endpoints for defined titers; removed the persistence endpoints for geometric mean titers (GMTs).
 

5 28 Feb 2022	N/A	
Table reduction initiative, including reducing redundancy
 
Adding additional analyses
 
Administrative changes
	
 
• Removed from Stage 2 analyses the exploratory 4-fold rise and the composite response endpoint for MenB strains.
 
• Replaced some study conduct tables for Stage 2 with listings in Section 6.6.
 
• Added exploratory analyses for MenA/C/W/Y to investigate the relationship between the pre-booster dose and the post-booster dose titers in Section 6.4.
 
• Added in Section 7.1 a new planned reporting event performed when subjects have completed the 1-month postbooster blood draw.
 
• Updated the temperature scale of severity for fever for Stage 2 (Table 14) in Section 3.5.2.2 to allow for consistency in severity designation between temperatures recorded in Fahrenheit and Celsius.
 
• Added the definition of the booster safety population in Section 4.4.
 

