##### **3.1.2. Primary Safety Endpoints**

The following endpoints will be described after Vaccinations 1 and 2 in the bivalent rLP2086 arms (Group 2 and 4 subjects) combined.

- Percentage of subjects reporting local reactions (pain, redness, and swelling) and by severity within 7 days after each vaccination visit.
- Percentage of subjects reporting systemic events (fever, vomiting, diarrhea, headache, fatigue, chills, muscle pain other than muscle pain at any injection site, and joint pain) and by severity within 7 days after each vaccination visit.
- Percentage of subjects reporting the use of antipyretic medications within 7 days after each vaccination visit.

- Percentage of subjects with at least 1 SAE during the following time periods:
  - 30 Days after each vaccination
  - 30 Days after any vaccination
  - During the Stage 1 vaccination phase (from the first study vaccination [Visit 1] through 1 month after the second study vaccination [Visit 4])
  - During the Stage 1 follow-up phase (from 1 month after the second study vaccination [Visit 4] through 6 months after the second study vaccination [Visit 5])
  - Throughout Stage 1 (from the first study vaccination [Visit 1] through 6 months after the second study vaccination [Visit 5])
  
- Percentage of subjects with at least 1 MAE occurring during the following time periods:
  - 30 Days after each vaccination
  - 30 Days after any vaccination
  - During the Stage 1 vaccination phase (from the first study vaccination [Visit 1] through 1 month after the second study vaccination [Visit 4])
  - During the Stage 1 follow-up phase (from 1 month after the second study vaccination [Visit 4] through 6 months after the second study vaccination [Visit 5])
  - Throughout Stage 1 (from the first study vaccination [Visit 1] through 6 months after the second study vaccination [Visit 5])
  
- Percentage of subjects with at least 1 NDCMC occurring during the following time periods:
  - 30 Days after each vaccination
  - 30 Days after any vaccination
  - During the Stage 1 vaccination phase (from the first study vaccination [Visit 1] through 1 month after the second study vaccination [Visit 4])
  - During the Stage 1 follow-up phase (from 1 month after the second study vaccination [Visit 4] through 6 months after the second study vaccination [Visit 5])
  - Throughout Stage 1 (from the first study vaccination [Visit 1] through 6 months after the second study vaccination [Visit 5])

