- Percentage of subjects with at least 1 AE occurring during the following time periods:
  - 30 Days after each vaccination
  - 30 Days after any vaccination
  - During the Stage 1 vaccination phase (from the first study vaccination [Visit 1] through 1 month after the second study vaccination [Visit 4])
- Percentage of subjects reporting at least 1 immediate AE after each vaccination.
- The number of days subjects missed school or work because of AEs during the Stage 1 vaccination phase (Visit 1 through Visit 4).

The following endpoints will be described after the booster vaccination in Groups 1 through 4:

- Percentage of subjects reporting local reactions (pain, redness, and swelling) and by severity within 7 days after the booster vaccination.
- Percentage of subjects reporting systemic events (fever, vomiting, diarrhea, headache, fatigue, chills, muscle pain other than muscle pain at any injection site, and joint pain) and by severity within 7 days after the booster vaccination.
- Percentage of subjects reporting the use of antipyretic medication within 7 days after the booster vaccination.
- Percentage of subjects with at least 1 SAE during the following time periods:
  - During the booster vaccination phase (from the booster vaccination [Visit 10] through 1 month after the booster vaccination [Visit 11])
  - During the booster follow-up phase (from 1 month after the booster vaccination [Visit 11] through 6 months after the booster vaccination [Visit 12])
  - From the booster vaccination (Visit 10) through 6 months after the booster vaccination (Visit 12)
- Percentage of subjects with at least 1 MAE occurring during the following time periods:
  - During the booster vaccination phase (from the booster vaccination [Visit 10] through 1 month after the booster vaccination [Visit 11])
  - During the booster follow-up phase (from 1 month after the booster vaccination [Visit 11] through 6 months after the booster vaccination [Visit 12])

- From the booster vaccination (Visit 10) through 6 months after the booster vaccination (Visit 12)
- Percentage of subjects with at least 1 NDCMC occurring during the following time periods:
  - During the booster vaccination phase (from the booster vaccination [Visit 10] through 1 month after the booster vaccination [Visit 11])
  - During the booster follow-up phase (from 1 month after the booster vaccination [Visit 11] through 6 months after the booster vaccination [Visit 12])

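### The Stage 1 fever scale has Celsius gaps at 101.2°F and 102.1°F, and the SAP closes them for Stage 2 only, so on unrounded values primary-series and booster fever severity use different cut-points

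*SAP*

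**What the plan says.** SAP 3.1.2 makes the severity of solicited systemic events, fever included, a primary safety endpoint in two settings. For the primary series, "The following endpoints will be described after Vaccinations 1 and 2 in the bivalent rLP2086 arms (Group 2 and 4 subjects) combined", with systemic events summarised overall "and joint pain) and by severity within 7 days after each vaccination visit". For the booster, "The following endpoints will be described after the booster vaccination in Groups 1 through 4", again by severity.

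Protocol 7.4.2.1 sets the grading: "Temperature will be measured and recorded to 1 decimal place and then categorized according to the severity scale" in Table 9. That table pairs Celsius and Fahrenheit bounds. Its second category reads "Temperature 38.5°C to 38.9°C (101.2°F to 102.0°F") and its third "Temperature 39.0°C to 40.0°C (102.1°F to 104.0°F"). The categories are not numbered; they are called 1 to 4 here, in order.

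SAP 3.5.2.2 drops the Fahrenheit bounds. Table 13 (Stage 1) runs 38.0-38.4, 38.5-38.9, 39.0-40.0 and >40.0°C. Table 14 (Stage 2) runs 38.0-38.4, >38.4-38.9, >38.9-40.0 and >40.0°C. On their use, the SAP says: "The original temperature scale (Table 13) was used in Stage 1 reporting and the updated temperature scale (Table 14) will be used" in the Stage 2 analyses. SAP Table 1 (version 5) gives the reason for the change: "to allow for consistency in severity designation between temperatures recorded in Fahrenheit and Celsius". No regrading of Stage 1 fever is described.

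**The concern.** The sponsor changed the fever scale because the earlier one did not treat Fahrenheit and Celsius readings consistently, then confined the change to Stage 2. Stage 1 fever severity is the primary safety endpoint for the licensed vaccine (Groups 2 and 4) and a secondary one for MenABCWY (Groups 1 and 3). If some Stage 1 fevers have no category, or a lower one than the protocol's Fahrenheit bounds give, the severity table does not follow the protocol.

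Reading across stages is also affected. SAP 6.2.2.1 plans reactogenicity summaries for Vaccination 1, Vaccination 2 and the booster, and SAP 6.7.1 allows graphs by dose. Primary-series and booster fever severity can therefore be shown side by side on different cut-points, and part of any difference could come from the scale.

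**Working it through.** **Inputs.** Category bounds from Protocol Table 9 and SAP Tables 13 and 14; recording precision of 0.1 degree from Protocol 7.4.2.1. Neither document fixes the recording unit or gives a conversion or rounding rule.

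**Step 1: reproduce Table 9's pairs.** Using °F = °C × 9/5 + 32:

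| °C | Exact °F | Table 9 |
|---|---|---|
| 38.0 | 100.40 | 100.4 |
| 38.4 | 101.12 | 101.1 |
| 38.5 | 101.30 | 101.2 |
| 38.9 | 102.02 | 102.0 |
| 39.0 | 102.20 | 102.1 |
| 40.0 | 104.00 | 104.0 |

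Four of the six pairs reproduce. The lower bounds of categories 2 and 3 do not: each stated Fahrenheit value is 0.1°F below the exact conversion.

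**Step 2: convert the two stated bounds back.** Using °C = (°F − 32) × 5/9:

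- 101.2°F: 69.2 × 5/9 = 38.444°C
- 102.1°F: 70.1 × 5/9 = 38.944°C

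**Step 3: grade both readings on each scale.**

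| Reading | Table 9 (°F) | Table 13, unrounded | Table 13, rounded to 0.1°C | Table 14, unrounded | Table 14, rounded to 0.1°C |
|---|---|---|---|---|---|
| 101.2°F | 2 | none | 1 | 2 | 1 |
| 102.1°F | 3 | none | 2 | 3 | 2 |

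**Step 4: look for other discrepancies.** Every 0.1°F reading from 100.0 to 106.0 was graded in the same way. With values unrounded or rounded to the nearest 0.1°C, only these two disagree with Table 9's Fahrenheit column. For every 0.1°C reading from 37.0 to 42.0, Tables 13 and 14 agree. Always rounding the conversion up would match Table 9 at both readings, but it would also turn 100.3°F (37.94°C) into 38.0°C, a fever, against the stated threshold of 100.4°F.

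**Step 5: extent.** Table 9's category 2 spans 9 possible 0.1°F readings (101.2 to 102.0) and category 3 spans 20 (102.1 to 104.0); one reading in each is affected. US sites supply 1320 of 1590 subjects (83%), which indicates how many might record in Fahrenheit, but the documents do not say how many did. They also give no fever rate, so no count of subjects follows.

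**The case against.** The strongest reply is that no misgrading can be shown. Table 9 carries Fahrenheit bounds, and if Stage 1 Fahrenheit entries were graded directly on them, nothing went wrong. SAP section 2 says programming rules are kept separately, so a conversion rule may exist there. This stands: the documents do not establish what was done. But SAP Table 13 shows no Fahrenheit bounds, and the sponsor's stated reason for Table 14 implies that the old scale could treat the two units differently.

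A reader might infer that Stage 1 graded these fevers one category too low and that Stage 2 then corrected this. No single rounding convention supports both. A lower grade requires rounding to 0.1°C, and at that precision Tables 13 and 14 grade identically, so Stage 2 would not correct it. The tables differ only on unrounded values, where Table 13 gives no category. Also, too low is meant only relative to Table 9's Fahrenheit column: 38.44°C and 38.94°C really are below 38.5°C and 39.0°C. The root is Table 9's inexact pairing.

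Nor is a planned statistic compromised. SAP Table 8 keeps the any-vaccination interval within Stage 1 and the booster separate, the planned group differences are within Stage 1, and SAP 5.2.1.3 says safety intervals test no hypothesis. The change of scale is disclosed, and leaving locked, reported Stage 1 results in place is defensible. These points limit the consequence. They do not supply the missing rule or put the two stages on one scale.

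**Conclusion.** The concern holds in a narrow form. Read literally, SAP Table 13 leaves 101.2°F and 102.1°F without a category, or puts them one category below Table 9's Fahrenheit column if values are first rounded to 0.1°C. The repair in Table 14 works only on unrounded conversions and covers Stage 2 only. On unrounded values, therefore, fever severity is a primary safety endpoint in both stages on different cut-points.

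The effect is confined to those two Fahrenheit readings. The number of subjects cannot be determined and is probably small; that is a judgement from the narrowness of the two readings, not an estimate. The documents do not support saying that Stage 1 fevers were in fact misgraded, or that any planned comparison is biased. The gap is in specification and traceability, and it is cheap to close.

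**What to change.** 1. Reconcile Protocol Table 9 with SAP Tables 13 and 14, so that the Celsius and Fahrenheit bounds describe the same categories.
2. State in SAP 3.5.2.2 that the Table 14 cut-points apply to unrounded converted temperatures. Without that condition, rounding first would undo the repair in Stage 2 as well.
3. Add to the Stage 2 report a supportive table of Stage 1 fever by severity on the Table 14 cut-points, with a footnote counting the subjects whose category differs from the Stage 1 report. The reported Stage 1 results stay as they are.

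The cost is a short SAP clarification and one extra table. A few Stage 1 subjects may move up one category or gain one. If the count is zero, the footnote settles the matter.

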### **3.5.2.3. Use of Antipyretic Medication**

The use of antipyretic medication will be recorded in the e-diary for 7 days (Day 1 to Day 7) after each vaccination.

The following variables will be derived:

1. Use of antipyretic medication on each day (Days 1 to 7) after each vaccination.
2. Use of antipyretic medication on any day (Days 1 to 7) after each vaccination and any vaccination.
3. Maximum duration of use of antipyretic medication after each vaccination.

## **3.6. Study Conduct**

### **3.6.1. E-Diary Completion**

For any given day, an e-diary will be transmitted and considered as complete if all expected data (the 3 local reactions and the 6 systemic events [including fever]) are available. If all data are missing for all items on the e-diary, for all days following vaccination, the e-diary will be considered not transmitted. An e-diary will be considered completed if all expected data for all days are available (ie, not missing) and data are valid. Otherwise, the e-diary will be considered incomplete. For any given day, an e-diary will be considered complete if all expected data are available.

The following e-diary compliance variables will be provided for each vaccination:

1. Compliance per day: the numerator is the number of subjects who completed (transmitted) the e-diary on a given day (Day 1 to Day 7) and the denominator is the total number of subjects who received the vaccination.
2. At least X day: the numerator is the number of subjects who completed (transmitted) the e-diary on any X day and the denominator is the total number of subjects who received a vaccination (X=1 through 7; compliance will be computed for each value of X).
3. All 7 days: the numerator is the number of subjects who completed (transmitted) the e-diary on all 7 days and the denominator is the total number of subjects who received a vaccination.

### **3.6.2. Nonstudy Vaccines and Concomitant Medications**

The name and date of administration of any nonstudy vaccine (or allergen immunotherapy) given from the signing of the informed consent document (ICD) up to Visit 11 will be recorded on the CRF. If the subject is known to have ever received a PRP-OMP vaccine, the name of the vaccine and date of administration will be recorded on the CRF. Similarly, if the subject has received any prior meningococcal vaccines or vaccines containing 1 or more ACWY group, the trade name (if known) and date of administration will be recorded on the CRF.

The name, start and stop dates, and route of administration for concomitant medications (prescription and nonprescription) used to treat an AE (excluding events recorded only in the e-diary) from the signing of the ICD to Visit 12 will be recorded in the CRF.

The use of antipyretic and other pain medications received by the subject on the day prior to investigational product administration will be recorded in the CRF.

Permitted during the study:

- Nonstudy vaccines used in the event of a disease outbreak or pandemic are allowed.
- Nonstudy vaccines (other than any meningococcal vaccines or vaccines containing 1 or more ABCWY groups, or vaccines containing all or individual antigens included in tetanus toxoid, reduced diphtheria toxoid and acellular pertussis vaccine, adsorbed [Tdap]) that are part of recommended immunization schedules are allowed any time during the study but should not be administered within 14 days (for nonlive vaccines) or 28 days (for live vaccines) of study vaccine administration.
- Antipyretic medication may be administered.
- A local anesthetic may be used at the site of blood draw.

- Topical antibiotics are permitted.
- Topical and inhaled corticosteroids are permitted.

Treatments will be categorized according to the current version (at the time of reporting) of the World Health Organization (WHO) Drug Dictionary.

#### **4. ANALYSIS SETS**

Data for all subjects will be assessed to determine if subjects meet the criteria for inclusion in each analysis population prior to unblinding and releasing the database and classifications will be documented per standard operating procedures.

The PAC population will include subjects in bivalent rLP2086 Groups 2 and 4 (bivalent rLP2086+MenACWY-CRM) only.

##### **4.1. Full Analysis Set**

A Stage 1 intent-to-treat (ITT) population will be defined and will include all subjects who are randomized at Visit 1. A Stage 2 ITT population will be defined as all subjects who signed the ICD at Visit 7.

##### **4.2. Modified Intent-to-Treat Population**

All randomized subjects who have received at least 1 study vaccination and who have at least 1 valid and determinate primary strain MenB or MenA/C/W/Y assay result available at any time point from Visit 1 to Visit 4 will be included in the modified intent-to-treat (mITT) population for Stage 1.

The mITT population for Stage 2 is defined as all subjects who signed the ICD at Visit 7 and who have at least 1 valid and determinate primary strain MenB or MenA/C/W/Y assay result available in Stage 2.

The mITT population will be analyzed according to the investigational product to which subjects were randomized (see handling of mis-stratified subjects in [Section 4.5](#)).

Subjects included in the pilot cohort will be included in the Stage 1 mITT population for immunogenicity analyses.

